11.3.3 Death Prior to Consent Being Sought

In the situation where a participant dies before consent has been sought, a site research team member will obtain information from colleagues and bereavement counsellors to establish the most appropriate research team member to notify the parents/legal guardians of the involvement in the research study. Parents/legal guardians can be given the information prior to their departure from the hospital, however, it is at the discretion of the site staff to determine if this is appropriate for each individual family. In this situation, the Participant Information Sheet for bereaved parents/legal guardians (B-PIS) would be used.

If the parent/legal guardian is not approached prior to their departure from the hospital, then they will be sent a covering letter, personalised by the most appropriate clinical team member, and a copy of the B-PIS (version for bereaved parents/legal guardians) by four weeks after randomisation. Where possible, the clinical team member should already be known to the family. The letter will explain how to opt out of the study, direct them to the B-PIS for detailed information on the study and provide telephone contact details if parents/legal guardians wish to discuss the study with a member of the site research team. The information can also be given to parents/legal guardians during follow-up appointments for bereaved parents (if conducted).

If no objection is received within four weeks of receipt of the letter, then the participant's data will be included in the study.

For this group of participants, the use of their confidential patient information (required for data linkage to NHS Digital and PICANet) will be conducted under the provisions of Section 251 of the National Health Service Act 2006 (subject to approval from the Confidentiality Advisory Group). The justification for requesting Section 251 support is that not being able to include information from patients who die very soon after enrolment, will result in a bias and may make one of the trial arms appear more beneficial than it actually is, or hide any indications of harm caused.

11.3.4 Non-Consent and Withdrawal

Parents/legal guardians can refuse to give consent (non-consent) or withdraw from the GASTRIC-PICU trial at any time during the study. If a parent/legal guardian explicitly states that they no longer wish for their child to take part or to contribute further data to the study, their decision must be respected. The date of withdrawal of consent and any reason, if provided, should be recorded onto the secure data entry system. A File Note documenting the withdrawal should be created and filed in the Investigator Site File. Withdrawal of a child from the study should be recorded in their medical notes and no further data collected. All data collected up to the point of withdrawal will be retained and included in the study analysis.

In order to monitor non-consent, a minimal dataset will be collected for each parent/legal guardian approached but not consented: a) Study site; b) Date/time randomised; c) Randomised intervention (including whether started on assigned treatment or not); d) Reason not consented (if parents/legal guardians are willing to provide reason for non-consent); e) Outcome at PICU discharge.

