16.3 Clinical effectiveness analysis methods

16.3.1 General principles

All analyses will be outlined in a statistical analysis plan (SAP) approved by an independent trial steering committee and seen by the independent data monitoring committee.

The following analysis populations will be defined:

- Per protocol (PP), which will exclude patients where consent to data collection has been withheld or withdrawn before day 30, and also patients classed as non-compliant as defined previously for the pilot evaluation stage.
- Intention to treat (ITT), which excludes patients where consent to data collection has been withheld or withdrawn for all data processing.
- ITT (energy intake), which excludes patients where consent to data collection has been withheld before 72 hours or withdrawn for all data processing.

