16.3.2 Analysis of co-primary clinical outcomes

The composite outcome will be analysed using a proportional odds logistic regression model, with death during the first 30 days following randomisation ranked as the worst possible outcome (assigned value -1), and surviving patients assigned values according to their total calendar days free from mechanical ventilation during the first 30 calendar days following randomisation (with the day of randomisation counted as day 1). The model will be adjusted for important baseline variables including all variables used as stratification variables at randomisation. Baseline factors for inclusion in adjusted analyses will be selected a priori based on an established relationship with outcome for critically ill children, and not because of observed imbalance, significance in univariable analyses or by a stepwise selection method. The proportional odds assumption will be tested using Brant's test; however, it is noted that in the event that the proportional odds assumption is violated, the odds ratio retains an equivalent interpretation to alternative effect estimates using non-parametric, rank-based methods. The primary effect estimate will be the adjusted odds ratio, which will be calculated in both the PP and ITT populations with two-sided 95% confidence intervals. If the upper limit of the confidence interval is not more than 1.2 in both the PP and ITT populations, we will declare the intervention is non-inferior with respect to mortality and days free of ventilation by 30 days. Secondary analyses will test the same outcome for superiority/inferiority. The two separate components of the composite primary outcome will also be reported by arm.

Percentage of energy requirements met will be calculated in the ITT population, and for each patient is defined as the total calories consumed during the first 72 hours divided by the target calorie intake for the first 72 hours (capped at 100%). The primary effect estimate will be the difference in mean percentage of target achieved between the arms, which will be tested for superiority (at P<0.05) using a linear regression model adjusted for the same baseline variables as the analysis of the composite primary outcome. The primary effect estimate will be the difference in means, which will be reported with a two-sided 95% confidence interval.

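### Section 11.3.4 has no withdrawal level short of ending all data collection, yet the ITT definition keeps early-withdrawn children whose 30-day outcome can then no longer be obtained

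*Protocol*

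**What the plan says.** Section 11.3.4 applies when a parent or guardian "explicitly states that they no longer wish for their child to take part or to contribute further data to the study". Two different wishes are joined there by a single "or"-type clause, and one consequence follows: "Withdrawal of a child from the study should be recorded in their medical notes and no further data collected". What was gathered before that moment is kept: "All data collected up to the point of withdrawal will be retained and included in the study analysis". Families who are approached and decline consent are handled separately. For them a short dataset is still recorded, ending with "e) Outcome at PICU discharge". No equivalent is given for families who withdraw.

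Section 16.3.1 defines the main analysis set as "Intention to treat (ITT), which excludes patients where consent to data collection has been withheld or withdrawn for all data processing". The PP set is narrower: it also removes children whose consent to data collection was withdrawn before day 30, and children who were non-adherent as defined in section 9.2.

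Section 16.3.2 ranks death within 30 days as worst, with "surviving patients assigned values according to their total calendar days free from mechanical ventilation during the first 30 calendar days following randomisation". Non-inferiority requires the upper 95% limit of the odds ratio to be no more than 1.2 in both PP and ITT.

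**The concern.** The three sections do not fit together. The ITT wording supposes that a family can withdraw to different degrees. Section 11.3.4 offers only one degree, and that one stops collection. A child withdrawn in the first 30 days, with earlier data kept, belongs to ITT but cannot be given a 30-day score.

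This matters because allocation is open (section 12.4) and consent is usually sought 24 to 48 hours after randomisation (section 11.3.1). A family can therefore decide knowing both the arm and how the child is doing. If withdrawal is related to both, the children who remain are a selected group and the odds ratio can move in either direction. The SAP may choose how to treat missing outcomes, but it cannot recover outcomes that the protocol stops collecting.

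The protocol accepts the principle elsewhere. Sections 11.3.2 and 11.3.3 justify Section 251 support by the bias that comes from leaving out particular groups. Much of the lost information is also routine: section 17.3 already draws on PICANet and death registrations, which need no further contact with the family.

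**Working it through.** **The same child under each section.** Take a child withdrawn on day 5, alive and still ventilated, whose family has not asked for earlier data to be removed.

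| Section | Consequence |
|---|---|
| 11.3.4 | Data to day 5 kept; nothing collected after |
| 16.3.1, ITT | Included: consent was given, and not withdrawn for all data processing |
| 16.3.1, PP | Excluded: withdrawn before day 30 |
| 16.3.2 | Needs survival and ventilation status to day 30: not available |

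The censoring rule in section 16.3.3 concerns when invasive ventilation ended and does not yield a 30-day ordinal score. The ITT set for energy intake has the same gap for withdrawal before 72 hours. Withdrawal after day 30 costs only 6-month data.

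**Plan's own figures (section 16.1).** Inputs: margin 1.2, 90% power, two-sided 95% interval, 4.2% mortality, log-normal ventilation with median 2.9 and lower quartile 1.0 days.
- Log-normal sigma = ln(2.9/1.0)/0.6745 = 1.58.
- Proportional-odds formula: N = 12(1.960 + 1.282)²/[ln(1.2)² × (1 − Σp³)]. With whole-day categories, 1 − Σp³ is 0.981 to 0.989 depending on how days are cut and whether the arms are averaged, giving N = 3,836 to 3,867. Power at 4,000 is about 91%, so the stated 4,000 is slightly conservative.
- Target: 4,000/0.85 = 4,706, or 4,000/(0.90 × 0.95) = 4,678. Both agree with 4,700.

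**Size of the withdrawn group.** 5% × 4,700 = 235. Losing them at random leaves 4,465 and power of about 93.6%, against 94.7% at 4,700. Precision is not the problem.

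**Illustration of bias.** Assumptions, none of them from the protocol: true odds ratio 1.2; every lost child comes from the worse half of that arm's outcomes; no outcome is imputed; the loss rates are as shown. The proportional-odds model is then fitted to the remaining distributions. With about 4,500 scored children in ITT, SE of the log odds ratio = √(12/(4,500 × 0.98)) ≈ 0.052. The estimate must be at or below 1.2/exp(1.96 × 0.052) ≈ 1.08 to pass. The chance of wrongly passing in ITT is Φ(ln(1.2/OR)/0.052 − 1.96).

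| Lost, intervention | Lost, control | Expected OR | ln(1.2/OR)/0.052 | False non-inferiority |
|---|---|---|---|---|
| 5% | 2% | 1.143 | 0.94 | about 15% |
| 5% | 4% | 1.181 | 0.31 | about 5% |
| 5% | 5% | 1.20 | 0.0 | about 2.5% |
| 2% | 5% | 1.261 | −0.95 | about 0.2% |

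These are ITT probabilities. PP must also pass, so the joint probability cannot be higher. PP corrects nothing, however, because it omits the same children by definition.

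**The case against.** A reader might infer that the protocol expressly ends follow-up for a parent who objects only to the allocated feeding approach. It does not name that parent. The trigger is a wish that the child no longer take part, which is leaving the trial. Section 9.2 also foresees departures from allocation without withdrawal, and those children stay in ITT with full outcomes. So a request to stop following the allocation need not be recorded as withdrawal. What stands is that section 11.3.4 gives no instruction for this case and has no intermediate level into which it could be placed.

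A reader might also infer that the bias favours non-inferiority. The documents do not establish a direction. Section 7.2 lists discomfort or mucosal damage from GRV measurement as a parental concern, which points, if anywhere, to withdrawal from the control arm. The last row of the table shows that this would make the test conservative.

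It can further be said that section 16.3.1 already hints at graded withdrawal and that the withdrawal form, which is not available here, may record levels. That is fair, and it would make the repair easier. It does not remove the conflict, because section 11.3.4 as written stops collection at any withdrawal.

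Finally, stopping all collection when a family leaves is a defensible position under research without prior consent. A refusal of further data must be respected. The point concerns only families who have not refused it.

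**Conclusion.** The mismatch between sections 11.3.4, 16.3.1 and 16.3.2 is established on the text and does not depend on any assumed rate. Children withdrawn before day 30 are kept in ITT without an obtainable primary outcome, and the dual PP and ITT requirement does not compensate.

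The effect on the result is possible but unquantified. Under the assumptions shown, false non-inferiority ranges from about 0.2% to about 15%, with no material shift when the arms lose equally. The differential rates and the worse-half selection are illustrations, not forecasts. The 235 children are a ceiling on what a fix could recover: families who refuse all further data remain lost, withdrawals after day 30 do not affect the primary outcome, and section 16.1 does not say how its 5% divides. This is an inexpensive improvement that should be made, not evidence that the trial's conclusion will be biased.

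**What to change.** Amend section 11.3.4 and the withdrawal form so that one of these levels is recorded:

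- (a) allocated approach no longer followed; data collection and linkage continue;
- (b) no further contact or questionnaires; routine-record collection and linkage continue;
- (c) no further data of any kind;
- (d) removal of all data.

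Only (c) and (d) stop collection. Align section 16.3.1 so that (a) and (b) stay in ITT with full outcomes, and decide their place in PP by the existing section 9.2 non-adherence definition.

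Cost: a protocol amendment, revised information-sheet and consent wording, one extra form field and a slightly longer conversation with families. No visits are added.

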11.3.5 Participants who turn 16 during PICU admission

This scenario is anticipated to occur infrequently, but should a participant turn 16 years of age during their PICU admission, the participant should be asked to provide their own consent (if they are assessed to have capacity). There is a specific Patient Information Sheet and Consent Form to be used in this scenario.

12. Trial Intervention

Daily nutritional goals in both intervention and control groups should be calculated based on the Schofield Equation, with the aim to achieve 65% of this target by 72 hours.

12.1 Intervention

The intervention arm is **no routine GRV measurement** to guide enteral feeding.

Patients should be monitored for signs of feed intolerance using clinical signs only: vomiting and other gastrointestinal or systemic signs but **not** by using GRV.

12.2 Comparator

The comparator (control arm) is routine (at least 6 hourly) GRV measurements to guide enteral feeding.

Patients should be monitored for feed intolerance using the GRV measurements as well as vomiting, and other gastrointestinal or systemic signs. The frequency of GRV should be as per standard local practice but should be at least 6 hourly. Further guidance can be found in Appendix 1 (Example Feeding Guidelines).

12.3 Concomitant Care

All other aspects of nutritional practice will be according to usual unit practice, including, but not limited to timing of commencement of feeds, speed of increase of enteral feeds and choice of feed.

12.4 Blinding

The GASTRIC-PICU trial is not a blinded trial, as it would not be practical to mask the different care pathways. Throughout the duration of the trial, only the trial statisticians and DMEC will see accumulating trial data by arm. Everyone else will remain blinded to this information until the final trial results are available.

12.5 Transferred Patients

If a randomised participant is transferred to another participating PICU, the new site should continue treatment according to the randomisation arm.

If a randomised participant is transferred to a non-participating PICU, then the randomising site should follow-up on the patient in order to obtain outcome data whenever possible.

12.6 End of Treatment

For both groups, trial treatment will continue until tube feeds have been discontinued during the PICU admission or until discharge from PICU, whichever is sooner. The trial treatment will apply at any point the patient requires tube feeds during their PICU admission (for example, the patient will return to their assigned treatment group in the case of failed attempt to stop tube feeding). The decision to discontinue tube feeds is at the discretion of the clinical team.

13. Trial Procedures

13.1 Summary of Data Collection

Data	Baseline	Day 3 (72 hrs)	Day 7	PICU discharge	Day 30	Hospital discharge	Month 6
Demographics	Х						
Energy/protein targets	Х	Х					
Enteral feeding data		Х	Х				
Feed tolerance data		Х	Х				
(e.g. vomiting)							
Diagnosis of VAP					Х		
Diagnosis of NEC					Х		
Healthcare-associated					Х		
infections							
Safety reporting		Х	Х	Х	Х		
Length of stay				Х		Х	
Mortality					Х		Х
PedsQL, CHU-9D							Х
(Quality of Life score)							
Feeding component of	Х						Х
the Functional Status							
Health Services							Х
Questionnaire (HSQ)							

13.2 Questionnaire follow-up

Each participant will be followed up with a questionnaire at 6 months post-randomisation to assess HRQoL and feeding status. Prior to the sending of questionnaire, survival status will be ascertained either through review of medical records by local research teams and/or via data-linkage with nationally held records (decedents will be logged in the trial records and the follow-up process ended).

At the 6-month time point, parents/legal guardians of recruited patients will be emailed or posted (as per their preference indicated at the time of consent) a questionnaire pack by the ICNARC CTU containing the PedsQL, CHU-9D, which will include a feeding status question (from the Functional Status Score), and a Health Services Questionnaire. If a parent requests the questionnaire to be sent via post, then a pen and self-addressed stamped envelope will be provided for ease of return.

If there is no response, parents/legal guardians will be telephoned and asked to confirm whether they have received the questionnaire. If needed, they will be offered the option of either being sent another copy of the questionnaire (via email or post), or to complete the questionnaires over the telephone with a trained member of the GASTRIC-PICU trial team.

If a patient is an in-patient at a participating site at the follow-up time-point, the site research team will be asked to approach the parent/legal guardian and, if willing, conduct the questionnaire with the parents/legal guardians in hospital.

14. Safety Reporting

Adverse Event (AE) reporting will follow the Health Research Authority guidelines on safety reporting in studies which do not use Investigational Medicinal Products (non-CTIMPs).

14.1 Definitions

Term	Definition			
Adverse Event	Any untoward medical occurrence or effect in a patient participating in a trial. It does not necessarily have to have a causal relationship with the trial intervention.			
Serious Adverse Event	 A serious adverse event is an untoward medical occurrence that: results in death is life-threatening* requires in-patient hospitalisation** or significant prolongation of existing hospitalisation results in persistent or significant disability/incapacity is a congenital anomaly/birth defect is otherwise considered medically significant by the Investigator. * "Life threatening" refers to an event in which the subject was at risk of death at the time of the event. It does not refer to an event that hypothetically might have caused death if it were more severe. ** "Hospitalisation", refers to inpatient admission, regardless of length of stay. This includes admission for continued observation. Any admission for pre-existing conditions that have not worsened, or elective procedures, do not constitute an SAE. 			
Serious Adverse Reaction	An adverse event that is both serious and, in the opinion of the reporting Investigator, believed with reasonable probability to be due to the trial intervention, based on the information provided.			
Unexpected and Related Serious Adverse Event	A suspected Adverse Event related (possibly, probably, or definitely) to the trial intervention that is both unexpected (i.e., not consistent with the expected outcomes of the treatment being offered) and serious.			

14.2 Assessment

The PI, or other medically qualified investigator as listed on the Delegation Log, should assess relatedness, expectedness and severity, categorised as follows:

14.2.1 Relatedness

None: there is no evidence of any causal relationship to the study treatment.

Unlikely: there is little evidence to suggest a causal relationship to the study treatment (e.g., because the event did not occur within a reasonable timeframe after administration of the trial treatment), and there is

another reasonable explanation of the event (e.g., the participant's clinical condition, other concomitant medications).

Possibly: there is some evidence to suggest a relationship to the study treatment (e.g., because the event occurred within a reasonable timeframe after administration of the trial procedure). However, the influence of other factors may have contributed to the event (e.g., the participant's clinical condition, other concomitant medications).

Probably: there is probable evidence to suggest a causal relationship to the study treatment, and the influence of other factors is unlikely.

Definitely: there is clear evidence to suggest a causal relationship to the study treatment, and other possible contributing factors can be ruled out.

14.2.2 Expectedness

Expected: the event is listed as an expected event in the Appendix 2.

Unexpected: the event is not listed as an expected event in the Appendix 2.

14.2.3 Severity

None: indicates no event or complication.

Mild: complications result in only temporary harm and do not require clinical treatment.

Moderate: complications require clinical treatment but do not result in significant prolongation of hospital stay. Does not usually result in permanent harm and where this does occur the harm does not cause functional limitations to the patient.

Severe: complications require clinical treatment and results in significant prolongation of hospital stay and/or permanent functional limitation.

Life threatening: complications may lead to death.

Fatal: indicates that the patient died as a direct result of the complication/adverse events.

14.3 Recording and Reporting Procedures

The key safety outcomes in the GASTRIC-PICU trial are ventilator-associated pneumonia (VAP) and necrotising enterocolitis (NEC). Incidence of these events will be captured via the Case Report Forms and does not need to be reported additionally as SAEs.

Considering that all children eligible for the GASTRIC-PICU trial are critically ill and, due to the complexity of their condition, are at an increased risk of experiencing AEs – occurrences of SAEs will only be reported if they are considered to be possibly, probably or definitely causally related to the study (i.e., either as a consequence of measuring GRV, or not measuring GRV). Non-serious adverse events do not require reporting for trial purposes.

The reporting period is from the time of randomisation until 30 days post-randomisation or until final discharge from critical care unit (whichever is sooner).

All reportable SAEs (i.e., serious events which are considered possible, probably, or definitely related to the study) must be reported to ICNARC CTU within 24 hours of the site research team becoming aware of the event. Related events must be assessed for expectedness (against the list in Appendix 3). Staff should not wait until all information about the event is available before sending SAE notification. Information not available at the time of the initial report must be documented and submitted as it becomes available.

SAEs must be recorded in the patients' medical notes and reported to the ICNARC CTU using the GASTRIC-PICU SAE Reporting eCRF. If the eCRF is unavailable, the SAE report can be sent by email to [contact].

The process for recording and reporting adverse events and serious adverse events is summarised in Figure 1 (Adverse Event Reporting).

Figure 1. Adverse Event Reporting

*If there is any uncertainty about whether the SAE is associated with trial treatment, then it should be reported.

On receipt of an SAE report, a member of the ICNARC CTU will first evaluate the report for completeness and consistency. Then, a clinical member of the GASTRIC-PICU Trial Management Group (TMG) will evaluate the event to determine whether it requires expedited reporting to the Research Ethics Committee (REC). If the event is a related and unexpected SAE, the ICNARC CTU will submit a report to the REC within 15 calendar days.

The ICNARC CTU will provide safety information to the Data Monitoring and Ethics Committee (DMEC) on a basis deemed appropriate by the DMEC.

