20,000 children aged 0-17 years were admitted to UK PICUs between 2016-2018. Around half of these were less than one year old (15). PICU is an expensive service with the average cost per day of > £2000 (16), so any intervention that has the potential to reduce the length of time spent on organ support in PICU is beneficial both for the child and family and for the health service. Intensive care nurse workload is also an area of increased scrutiny, given nurses are the largest human cost in a PICU, therefore reducing nursing workload by removing any unnecessary practice would be beneficial. Furthermore, as 96.5% children now survive critical illness in the UK (15), ensuring the best possible outcomes is paramount. We know that nutritional deterioration *during* critical illness is frequent and intense (17) with both short- and long-term consequences. Thus, the effect of this practice may increase as PICU stay increases. This is important because the proportion of long-stay PICU patients in UK PICUs (and corresponding bed days) has increased significantly in the last 15 years (18).

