16.1 Sample Size Calculation

For the composite outcome, a non-inferiority margin of an upper limit for the odds ratio of 1.2 was selected (corresponding to a 0.8% absolute increase in mortality and a 12-hour difference in median duration of ventilation). In a survey of UK PICU clinicians this margin was preferred because it would have a meaningful impact on duration of PICU admission and it is a change that would be highly relevant to patients/families. To have 90% power to detect non-inferiority, based on the upper limit of a two-sided 95% confidence interval excluding this margin, and using an outcome distribution estimated from the SANDWICH trial (4.2% mortality and log-normal distribution for duration of ventilation with median 2.9 days and lower quartile 1.0 days) requires a total evaluable sample size of 4000. To retain power for a perprotocol analysis we have allowed for cross-over of 10% and withdrawal of 5%, to set a total target size of 4700.

The percentage of the child's predicted energy requirements achieved by 72 hours after randomisation is anticipated to be approximately normally distributed, with standard deviations within each arm between 20 and 40% (22). The planned sample size in the intention-to-treat population will therefore provide >90% power (at P<0.05, two-sided) to detect a 4% absolute difference in energy intake based on the most conservative assumption of a standard deviation of 40%.

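### Related-SAE reporting stops at day 30 while allocated treatment can continue for as long as a child is tube-fed in PICU, and the protocol contradicts itself on whether VAP, NEC and infections are recorded after that day

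*Protocol*

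**What the plan says.** **Safety window.** Section 14.3: "The reporting period is from the time of randomisation until 30 days post-randomisation or until final discharge from critical care unit (whichever is sooner". Only SAEs judged possibly, probably or definitely related to measuring or not measuring GRV are reportable. VAP and NEC are named as the key safety outcomes. They are captured on the CRF and need no separate SAE report.

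**Treatment period.** Section 12.6: "For both groups, trial treatment will continue until tube feeds have been discontinued during the PICU admission or until discharge from PICU, whichever is sooner". It adds: "The trial treatment will apply at any point the patient requires tube feeds during their PICU admission". No day limit is given.

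**Capture of VAP, NEC and infections.** Section 8.3.2 lists these among the secondary outcomes of the PICU stay, with no day limit. The section 13.1 schedule marks each of them once, in the day 30 column.

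**Other data after day 30.** Mortality is collected at 6 months. Length of PICU and hospital stay are recorded without a cap. Quality of life and feeding status are collected at 6 months.

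**Planning distribution.** Section 16.1 assumes "4.2% mortality and log-normal distribution for duration of ventilation with median 2.9 days and lower quartile 1.0 days".

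**The concern.** The two periods do not match. For a child who leaves PICU before day 30, the SAE window covers the whole time on trial treatment. For a child still tube-fed in PICU on day 31, it does not: the allocation still governs care, but a serious event that the investigator attributes to it is no longer reportable.

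The 24-hour report to the CTU and the 15-day report of related unexpected events to the ethics committee both start from the site's duty to report. So does the SAE information that the CTU can pass to the DMEC.

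The usual reason for a short window is to avoid a flood of events from critically ill children. Section 14.3 has already dealt with that by making only related SAEs reportable. What the cap removes is therefore exactly the events attributed to the strategy.

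The CRF does not clearly fill the gap. From sections 8.3.2 and 13.1 together, a site cannot tell whether an NEC diagnosed on, say, day 35 in PICU should be recorded. At stake is whether the trial's safety statement covers the treatment period that its protocol prescribes.

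**Working it through.** **1. The periods side by side**

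| Item | Ends at | Section |
|---|---|---|
| Allocated strategy | end of tube feeds in PICU, or PICU discharge; resumes with tube feeding | 12.6 |
| Related-SAE reporting | earlier of day 30 and final critical care discharge | 14.3 |
| VAP, NEC, infections | the PICU stay, no day limit | 8.3.2 |
| VAP, NEC, infections | day 30 | 13.1 |
| Mortality | 6 months | 8.3.2, 13.1 |

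For a child tube-fed in PICU on day 31, row 1 is open, row 2 is closed, rows 3 and 4 disagree, and row 5 is open.

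**2. Reproducing the plan's own figure**

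This confirms that the section 16.1 distribution has been read as intended. The inputs are 4.2% mortality, median 2.9 days and lower quartile 1.0 days. The margin is given as "non-inferiority margin of an upper limit for the odds ratio of 1.2 was selected", with 90% power and a two-sided 95% interval.

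- Log-normal: mu = ln 2.9; sigma = ln(2.9/1.0)/0.6745 = 1.579.
- Proportional-odds sample size (Whitehead): N = 12(1.960 + 1.282)²/[(ln 1.2)² × (1 − Σp³)]. Here p runs over death and the ventilation-day categories.
- Without the Σp³ term, N = 3,793. With it, N is 3,842 to 3,939, depending on how days are grouped (Σp³ from 0.013 to 0.037).
- Power at the stated 4,000 is 90.4% to 91.1%.
- Inflation: 4,000/(0.90 × 0.95) = 4,678, or 4,000/0.85 = 4,706, against the stated 4,700.

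The plan's figures are reproduced closely enough to use the distribution.

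**3. Share still ventilated at day 30**

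- P(T > 30) = 1 − Φ(ln(30/2.9)/1.579) = 1 − Φ(1.480) = 0.0694, or 6.9% of survivors.
- As a share of all randomised: 0.958 × 0.0694 = 6.65%.
- Children: 4,700 × 0.0665 = about 313.

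**4. Sensitivity**

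- Cut-off at 29 or 31 days: 7.2% or 6.7%.
- Rounding of the stated quantiles: a median of 2.85 with lower quartile 1.05 gives 5.6%, and 2.95 with 0.95 gives 8.4%. In children, 4,700 × 0.958 × 0.056 = 252 and 4,700 × 0.958 × 0.084 = 378.
- Section 16.1 does not say whether the distribution is for survivors only. If it applies to all randomised, the count is 4,700 × 0.0694 = 326.

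**5. What the share measures**

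It measures ventilation, not tube feeding or PICU stay, for which the protocol gives no figure beyond day 30. Children extubated but still tube-fed in PICU would add to it. Ventilated children no longer fed by the gastric route would reduce it.

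**The case against.** Several points can fairly be made for the plan.

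- **Harm is not unobserved after day 30.** Mortality to 6 months is compared between arms by logistic and Cox models (16.3.3). PICANet supplies daily critical care interventions for the index admission and readmissions (17.3). Reported events are followed to resolution (14.5). The DMEC decides on what basis it receives safety data and may ask for further interim analyses (15.3). All this stands, so a reader who infers that no harm is reported after day 30 goes too far. But all-cause mortality carries no relatedness assessment and misses non-fatal events, and the DMEC cannot review related SAEs that sites had no duty to report.
- **VAP and NEC are not governed by the SAE window.** They go through the CRF at every time point, and Appendix 2 lists them as expected, so day 30 changes nothing about expedited reporting of them. Sections 8.3.2 and 8.3.3 give them no cap. This also stands: their position is a contradiction between 8.3.2 and 13.1, not a proven loss. A count of VAP episodes missed, from the section 7.1 rates and the ventilator-days after day 30, would assume that the contradiction resolves one way and that the extrapolated tail holds.
- **Section 7 does not say that harm grows with stay.** Its remark that "the effect of this practice may increase as PICU stay increases" follows from a sentence on nutritional deterioration. A reader might infer a rising risk of aspiration, VAP or NEC from not measuring GRV, but the text does not say so.
- **The tail is extrapolated.** A median and a lower quartile fix it, with no upper-tail figure. Eligibility pushes it both ways: section 10.1 requires that extubation is not planned within 48 hours, and section 10.2 excludes long-term ventilation.
- **The 30-day window matches the composite primary endpoint**, in a trial that section 18.2 rates as minimal risk. That supports a 30-day comparison between arms. It does not explain ending the duty to report related events while treatment goes on.

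**Conclusion.** The mismatch between 12.6 and 14.3 stands on the text alone and needs no assumption. Following the protocol exactly, a related SAE after day 30 in a child still tube-fed in PICU is not reportable. The conflict between 8.3.2 and 13.1 on VAP, NEC and infections also stands. Mortality to 6 months is the only harm clearly captured after day 30.

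The size is about 7% of survivors still ventilated at day 30, or about 6% to 8% with rounding: roughly 300 of 4,700 children. This assumes that the section 16.1 log-normal holds in its tail, and it is only a proxy for children still on trial treatment. A reader might take it as the share remaining on their allocated arm, but the protocol has no figure to support that. Even at half this share, more than 150 children would be affected.

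The primary analysis is untouched. The point should be amended because safety conclusions would otherwise not cover the treatment period that the protocol prescribes.

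**What to change.** - **Section 14.3:** delete the 30-day cap, so that related SAEs are reportable from randomisation until final discharge from critical care. Do not tie the window to the end of trial treatment in 12.6. A child who stops tube feeds on day 5 but stays in PICU to day 20 is covered to day 20 now and would lose cover from day 5.
- **Sections 8.3.2 and 13.1:** reconcile them so that VAP, NEC and healthcare-associated infections are recorded to PICU discharge for children still in PICU at day 30. Carry the safety reporting row of 13.1 to the same point.
- **Reporting:** keep the 30-day count as the between-arm comparison, since later follow-up depends on length of stay. List later events by arm for the DMEC.

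The change concerns data collection only and leaves treatment as it is. The cost is protocol and CRF wording, plus a small amount of extra CRF and SAE reporting for the long-stay minority. No new procedure is needed.
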